#### 3.2 Secondary Analysis: Nested Mixed Effect Models

We will calculate the effect of the filter on the difference between time point 1(T1) and time point 2 (T2), time point 3 (T3), and time point 4 (T4) to see how early any effect appears and characterize the temporal pattern of the response.

For In-HF HRV, skin conductance levels, and self-reported stress:

Null model:

$$Y_{its} = \beta_0 + \beta_1 baseline_{is} + \beta_2 T 2_{is} + \beta_3 T 3_{is} + \beta_4 T 4_{is} + \alpha_i + \varepsilon_{its}$$

- Where:
  - $Y_{its}$  is the observed average outcome for individual *i*, at time point *t* where *t* is T1, T2, T3, or T4, and session *s* where *s* is session 1 or session 2
  - $\beta_0$  is the value of  $Y_{its}$  at T1 and adjusted for baseline.
  - $\beta_1$  is the estimated difference in  $Y_{its}$  at T1, T2, T3, or T4 between two groups differing in baseline by 1 unit.
  - $\circ$   $\beta_2$  is the difference between  $Y_{its}$  comparing T1 and T2, adjusted for baseline.
  - $\circ$   $\beta_3$  is the difference between  $Y_{its}$  comparing T1 and T3, adjusted for baseline.
  - $\beta_{4}$  is the difference between  $Y_{its}$  comparing T1 and T4, adjusted for baseline.
  - $\alpha_i$  is the random intercept for subjects to account for repeated measures within individuals
  - $\varepsilon_{its}$  is the observation-specific error

Full model:

 $Y_{its} = \beta_0 + \beta_1 baseline_{is} + \beta_2 T 2_{is} + \beta_3 T 3_{is} + \beta_4 T 4_{is} + \beta_5 filter_{is} + \beta_6 T 2_{is} * filter_{is} + \beta_7 T 3_{is} * filter_{is} + \beta_8 T 4_{is} filter_{is} + \alpha_{is} + \varepsilon_{its}$ 

- Where:
  - $Y_{its}$  is the observed average outcome for individual *i*, at time point *t* where *t* is T1, T2, T3, or T4, and session *s* where *s* is session 1 or session 2
  - $\beta_0$  is the average  $Y_{its}$  at T1 and adjusted for baseline for the study population when they were assigned the A filter.
  - $\beta_1$  is the estimated difference in  $Y_{its}$  at T1, T2, T3, or T4 between two groups differing in baseline by 1 unit.
  - $\beta_2$  is the average difference in  $Y_{its}$  comparing T1 and T2 for the study population when they were assigned the A filter, adjusted for baseline.
  - $\beta_3$  is the average difference in  $Y_{its}$  comparing T1 and T3 for the study population when they were assigned the A filter, adjusted for baseline.

- $\beta_4$  is the average difference in  $Y_{its}$  comparing T1 and T4 for the study population when they were assigned the A filter, adjusted for baseline.
- $\beta_5$  is the average difference between  $Y_{its}$  at T1 when the study population was assigned the A filter and  $Y_{its}$  at T1 when they were assigned the B filter, adjusted for baseline.
- $\beta_6$  is the average difference between  $Y_{its}$  at T2 when the study population was assigned the A filter and  $Y_{its}$  at T2 when they were assigned the B filter, adjusted for baseline.
- $\beta_7$  is the average difference between  $Y_{its}$  at T3 when the study population was assigned the A filter and  $Y_{its}$  at T3 when they were assigned the B filter, adjusted for baseline.
- $\beta_8$  is the average difference between  $Y_{its}$  at T4 when the study population was assigned the A filter and  $Y_{its}$  at T4 when they were assigned the B filter, adjusted for baseline.
- $\alpha_i$  is the random intercept for subjects to account for repeated measures within individuals
- $\varepsilon_{its}$  is the observation-specific error

For positive and negative affect levels (SF-PANAS):

Null model:

 $Y_{its} = \beta_0 + \beta_1 baseline_{is} + \beta_2 T2_{is} + \beta_3 T3_{is} + \beta_4 T4_{is} + \beta_5 missingscaleitems_{is} + \alpha_i + \varepsilon_{its}$ 

- Where:
  - $Y_{its}$  is the observed average outcome for individual *i*, at time point *t* where *t* is T1, T2, T3, or T4, and session *s* where *s* is session 1 or session 2
  - $\beta_0$  is the value of  $Y_{its}$  at T1 and adjusted for baseline and missing scale items.
  - $\beta_1$  is the estimated difference in  $Y_{its}$  at T1, T2, T3, or T4 between two groups differing in baseline by 1 unit, adjusted for missing scale items.
  - $\beta_2$  is the difference between  $Y_{its}$  comparing T1 and T2, adjusted for baseline and missing scale items.
  - $\beta_3$  is the difference between  $Y_{its}$  comparing T1 and T3, adjusted for baseline and missing scale items.
  - $\beta_4$  is the difference between  $Y_{its}$  comparing T1 and T4, adjusted for baseline and missing scale items.
  - $\beta_5$  is the estimated difference in  $Y_{its}$  between two groups differing in missing affect scale items by 1 item, adjusted for baseline.
  - $\alpha_i$  is the random intercept for subjects to account for repeated measures within individuals
  - $\circ$   $\varepsilon_{its}$  is the observation-specific error

Full model:

$$Y_{its} = \beta_0 + \beta_1 baseline_{is} + \beta_2 T2_{is} + \beta_3 T3_{is} + \beta_4 T4_{is} + \beta_5 filter_{is} + \beta_6 T2_{is} * filter_{is} + \beta_7 T3_{is} * filter_{is} + \beta_8 T4_{is} filter_{is} + \beta_9 missingscale items_{is} + \alpha_{is} + \varepsilon_{its}$$

- Where:
  - $Y_{its}$  is the observed average outcome for individual *i*, at time point *t* where *t* is T1, T2, T3, or T4, and session *s* where *s* is session 1 or session 2
  - $\beta_0$  is the average  $Y_{its}$  at T1 and adjusted for baseline and missing scale items for the study population when they were assigned the A filter.
  - $\beta_1$  is the estimated difference in  $Y_{its}$  at T1, T2, T3, or T4 between two groups differing in baseline by 1 unit, adjusted for missing scale items.
  - $\beta_2$  is the average difference in  $Y_{its}$  comparing T1 and T2 for the study population when they were assigned the A filter, adjusted for baseline and missing scale items.
  - $\beta_3$  is the average difference in  $Y_{its}$  comparing T1 and T3 for the study population when they were assigned the A filter, adjusted for baseline and missing scale items.
  - $\beta_4$  is the average difference in  $Y_{its}$  comparing T1 and T4 for the study population when they were assigned the A filter, adjusted for baseline and missing scale items.
  - $\beta_5$  is the average difference between  $Y_{its}$  at T1 when the study population was assigned the A filter and  $Y_{its}$  at T1 when they were assigned the B filter, adjusted for baseline and missing scale items.
  - $\beta_6$  is the average difference between  $Y_{its}$  at T2 when the study population was assigned the A filter and  $Y_{its}$  at T2 when they were assigned the B filter, adjusted for baseline and missing scale items.
  - $\beta_7$  is the average difference between  $Y_{its}$  at T3 when the study population was assigned the A filter and  $Y_{its}$  at T3 when they were assigned the B filter, adjusted for baseline and missing scale items.
  - $\beta_8$  is the average difference between  $Y_{its}$  at T4 when the study population was assigned the A filter and  $Y_{its}$  at T4 when they were assigned the B filter, adjusted for baseline and missing scale items.
  - $\beta_9$  is the estimated difference in  $Y_{its}$  at T1, T2, T3, or T4 between two groups differing in missing affect scale items by 1 item, adjusted for baseline.
  - $\alpha_i$  is the random intercept for subjects to account for repeated measures within individuals
  - $\varepsilon_{its}$  is the observation-specific error

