## 4. Data Exclusions

## 4.1 Handling Missing Data

We assessed missing data after obtaining a blinded dataset but before being unblinded to the actual treatment per session. Unexpected missing data emerged in the blinded dataset, resulting in the absence of a predefined approach to address this issue prior to data collection. Primary analysis will use a complete case dataset, except for the positive and negative affect outcome. 16 (3.9%) of the 414 questionnaires

were missing 1-2 items at one of the time points, and the impact of missing items will be adjusted for using the number of missing items variable in the model.

We expect the small amount of missingness to have a minimal impact on our results, however we will assess this impact with sensitivity analyses. For comparison, we will perform the analysis on an imputed dataset. We expect this to narrow confidence intervals without greatly impacting the coefficient.

We will be imputing some missing values for two types of data, 1) missing questionnaire items (relevant to secondary outcomes) and 2) missing baseline ln-HF HRV (relevant to primary outcome). The PANAS positive affect (PA) and negative affect (NA) outcomes are scored by summing 5 individual PA and NA items. 16 (3.9%) of the 414 questionnaires were missing 1-2 items at one of the time points, though the data were typically complete for other time points. Because answers for the same item are modestly correlated between timepoints from the same day (mean  $R^2 = 0.58$ ), but still performed better than other imputation approaches (random PA and NA item from the day, mean PA or NA score, and regression imputation), we will use the mean available item value for missing items. This methodology is similar to the mean imputation approach demonstrated in Shrive et al. (2006), but employs individual item row mean imputation, a single item imputation approach that can be used for longitudinal data (Engels and Diehr, 2003).

Brief State Rumination Inventory (BSRI) is a sum of 8 individual items. 6 (4.3%) of the 138 questionnaires were missing 1-2 items. The answers for the same item were correlated with the other time point for the same day (mean  $R^2 = 0.83$ ).

For ln-HF HRV, there were 5 participants whose ln-HF HRV was partially captured both before and during exposure, but missing during the window of our standard baseline time (i.e., B1).

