Additional 5-minute periods of ln-HF HRV were calculated using continuous data from before treatment exposure, including 10-5 minutes before B1 (R1), 5-0 minutes before B1 (R2), 0-5 minutes into the venipuncture procedures (V1), 5-10 minutes into the venipuncture procedure (V2), 0-5 minutes into the drive up to the forest site (D1), and 5-10 minutes into the drive up to the forest site (D2).

Correlations between B1 ln-HF HRV and each additional time point prior to exposure were assessed using a complete case data set.

Time points with the highest correlations (R1, R2, V1, D1) were included in single linear regression models to predict B1 values using a complete case data set. One participant did not have any additional timepoints available, so we used a regression model with the B1 measurement from the other session as a predictor ( $s_{b1}hrv \sim s_{b1}hrv$ ).

Each single linear regression model (b1\_hrv ~ r1\_hrv, b1\_hrv ~ r2\_hrv, b1\_hrv ~ v1\_hrv, b1\_hrv ~ d1\_hrv, s2\_b1\_hrv ~ s1\_b1\_hrv) was cross validated using a complete-case dataset to assess  $R^2$  values (0.92, 0.95, 0.98, 0.85, and 0.83, respectively).

Models were preferentially ranked based on R^2 values and predicted values for B1 will be imputed depending on R1, R2, V1, D1, and S1B1 (session 1 baseline 1) timepoint availability. Of the missing

baseline observations, there is one person for whom we would use V1 to predict B1, three people for whom we would use D1 to predict B1, and one person for whom we would use S1B1 to predict S2B1.

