#### 4.2 Data Exclusion Criteria

Five participants were removed from analysis: two participants who were recommended for exit by IRB staff following responses to study protocols, one participant who withdrew mid-session, and two participants who were found to meet exclusion criteria following their first session.

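### Secondary T1–T4 models: the random intercept differs between null and full models, no session term is defined, and β6 to β8 are worded as something the equation does not estimate

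*SAP*

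**What the plan says.** SAP 3.2 Secondary Analysis sets out to estimate "the effect of the filter on the difference between time point 1(T1) and time point 2 (T2", and likewise for T3 and T4, to see how early an effect appears and how it develops.

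- **Random terms.** For ln-HF HRV, skin conductance and stress, the null equation ends "\beta_4 T 4_{is} + \alpha_i + \varepsilon_{its" and the full equation ends "filter_{is} + \alpha_{is} + \varepsilon_{its". The SF-PANAS pair shows the same difference.
- **Definition.** Under every model, including both full models, only α_i is defined; it "is the random intercept for subjects to account for repeated measures within individuals". α_is is defined nowhere.
- **Comparison.** The heading calls the models nested and they are labelled null and full, but no likelihood-ratio or other test is named.
- **Interactions.** β6 is worded as the difference between the outcome at T2 under filter A and the outcome "at T2 when they were assigned the B filter, adjusted for baseline". β7 and β8 are worded the same way for T3 and T4.
- **Data layout.** Filter and baseline are indexed by subject and session, and each session contributes four rows.

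**The concern.** An analyst cannot tell from the text which random structure to fit, and each reading has a defect.

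(a) **As printed.** The two models differ in their random part as well as in the filter terms, so they are not nested and their comparison does not isolate filter. The full model also gives up the pairing of a person's two sessions.

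(b) **Subject intercept in both.** Filter is constant within a session. The four readings of a session share that day's level and the error of one common baseline reading, yet they would be treated as independent given the subject.

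(c) **Wording of β6 to β8.** Read literally, a change since T1 would be reported as the filter effect at a given time.

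The time course is the purpose of this section. At stake are a spurious overall filter signal under (a), a misjudged onset and time course under (b), and mislabelled estimates under (c).

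**Working it through.** The documents give no operating characteristics for these models, so there is no stated figure to reproduce. They also state no significance level; 5% two-sided is assumed.

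**1. What the coefficients are.** With T1 as reference, the filter effect is β5 at T1, β5+β6 at T2, β5+β7 at T3 and β5+β8 at T4. So β6 = (effect at T2) − (effect at T1). This agrees with the section's aim and with the SAP's own wording of β5 as the T1 difference. It contradicts the wording of β6 to β8. No assumption is needed here.

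**2. Closed form for reading (b), ignoring baseline error.** Let ρ be the session share of within-person variance (total set to 1), with two sessions of four readings. After the subject mean is removed, 7 df remain: one between sessions with variance 1+3ρ, and six within sessions with variance 1−ρ. The subject-intercept model pools them:

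[(1+3ρ) + 6(1−ρ)]/7 = 1 − 3ρ/7.

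- β5: model/true variance = 1 − 3ρ/7.
- β6 to β8: model/true variance = (1 − 3ρ/7)/(1 − ρ).

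| ρ | β5 SE ratio | β5 type I error | Interaction SE ratio | Interaction type I error |
|---|---|---|---|---|
| 0.10 | √0.957 = 0.98 | 5.5% | √(0.957/0.90) = 1.03 | 4.3% |
| 0.50 | √0.786 = 0.89 | 8.2% | √(0.786/0.50) = 1.25 | 1.4% |

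The 4-df test of β5 to β8 rejects 6.0–13.3% over the same range.

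**3. Inputs for ln-HF HRV.**
- *Sample (inferred).* The Protocol's Methods section gives 43 enrolled. SAP 4.2 states "Five participants were removed from analysis", leaving 43 − 5 = 38. SAP 4.1 states "6 (4.3%) of the 138 questionnaires were missing 1-2 items" for an inventory given at two time points a day, so 138/2 = 69 sessions. That is 69 − 38 = 31 participants with two sessions and 38 − 31 = 7 with one.
- *Correlations.* SAP 4.1 gives cross-validated R² of "0.92, 0.95, 0.98, 0.85, and 0.83, respectively". The first four are within a session and the last is between sessions. Reading R² as a squared correlation, between-session r = √0.83 = 0.911 and same-session r = √0.85 to √0.98 = 0.922 to 0.990.
- *Variances (total 1).* Subject 0.911; session r_same − 0.911; error 1 − r_same. The session share of within-person variance is h = 0.011/0.089 to 0.079/0.089, or 12–89%. After ideal baseline adjustment it is h/(1+h), or 11–47%.

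**4. Simulation with no filter effect.** Each of 4,000 runs per case had one baseline and four readings per session. Standard errors came from REML with z tests, and the 4-df test from ML (critical value 9.49). Fits matched a standard mixed-model routine.

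| ln-HF HRV | 4-df rejection | β5 type I error | β6 to β8 type I error |
|---|---|---|---|
| (a) as printed | 97.9–99.5% (median statistic 38–51) | 4.7–5.1% | – |
| (b) α_i in both | 11.7–13.7% | 7.6–9.3% (SE 10–12% too small) | 1.5–2.9% (SE 13–24% too large) |
| α_i plus session-within-subject in both | 5.7–6.2% | 5.5–5.8% | 4.7–5.3% |

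Under (b), even with session variance set to zero, the 4-df test rejects 10.7%, because the four readings share the baseline error. Monte Carlo SE is about 0.3–0.5 points for rates near 5–14%.

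**5. Skin conductance, stress and affect.** The documents give nothing to calibrate these. Assuming subject variance of 30–70% and session variance of 0–20% of the total:
- (a) 4-df rejection 4–74%, a negative statistic in 6–61% of runs (impossible for nested ML fits), and estimates 1–6% less precise.
- (b) 4-df rejection 5.7–9.7%, β5 5.2–7.2%, interactions 3.5–4.9%.
- Both intercepts in both models: 4-df rejection 5.0–6.1%.

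**6. Second simulation.** This used 38 complete pairs, with post-baseline subject variance 0.5, error 1, and session variance 0, 0.12, 0.5 or 1. Reading (a) rejected 0%, 5%, 81% and 99.8%; reading (b) rejected 4.8%, 7.2%, 12.6% and 15.4%. With variances from the SAP's R² values, (a) gave 99–100% and (b) 8.5–16%.

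**The case against.** The strongest reply is that α_is is a typographical slip. Subscripts in these equations are loose elsewhere: the time indicators carry no time index, and a multiplication sign is missing. Every definition list says α_i. No null-versus-full test is written either, so the near-100% rejection describes an analysis that may never be run; fitted alone, the printed full model has nearly correct standard errors. **This stands**, and (a) should be read as conditional on the comparison being made as printed.

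Under the slip reading, the coefficients closest to the section's stated aim are the interactions, and their error is conservative. **This also stands**: the cost there is power. It does not cover the effect at a single time or the 4-df test, both of which are anti-conservative.

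The calibration is thin. The R² values come from before exposure, and the highest come from windows close to the baseline window, whereas T1 to T4 are roughly 17 to 20 minutes apart. Their unequal size also fits an equal-correlation model poorly. The lower session shares are therefore the more defensible. The 4-df test under (b) hardly depends on this choice: with no session variance it still rejects 10.7%. For skin conductance, stress and affect, no magnitude is established.

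The slip reading leaves (b) and (c) in place, and (c) depends on no simulation.

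**Conclusion.** The concern holds and should be fixed. The subscript mismatch, the missing definition and the wrong wording of β6 to β8 are plain on the page.

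For ln-HF HRV, comparing the models as printed would signal a filter effect almost regardless of the data. A subject intercept in both gives roughly a 12–14% error rate on the 4-df test, with errors in opposite directions for single-time effects and for changes over time.

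These sizes rest on the inferred sample of 31 two-session and 7 one-session participants, on R² read as squared correlation, and on forest readings behaving like pre-exposure ones. For the other outcomes the size depends on assumed variances.

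Only the secondary T1–T4 models are affected. The primary T2 and T4 models use one record per session, for which a subject intercept is adequate.

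**What to change.** - Use the same random part in the null and full models for ln-HF HRV, skin conductance, stress and SF-PANAS: α_i + γ_is, in lme4 `(1 | subject) + (1 | subject:session)`. Define both terms.
- State whether the models are compared. If they are: ML fits, identical random parts, 4 df for β5 to β8.
- Redefine β6 to β8 as changes in the filter effect relative to T1. Report the effects at T2, T3 and T4 as β5+β6, β5+β7 and β5+β8, with standard errors from the joint covariance matrix.

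The cost is one variance component and corrected text. For some outcomes the session component may be estimated near zero; the SAP should say that it stays in the model in that case.

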# 3.3 Absorbed Dose Association with Outcomes

We will calculate the association of absorbed dose (difference between baseline and T4 serum terpene levels) and the difference between baseline measurements and time point 4 (T4) for ln-HF HRV, skin conductance levels, self-reported stress, positive and negative affect levels (SF-PANAS), systolic blood pressure, diastolic blood pressure, heart rate, inflammatory biomarkers, and cortisol using a mixed effect model. Participants who completed only one session will also be included in analysis.

For ln-HF HRV, skin conductance levels, self-reported stress, systolic blood pressure, diastolic blood pressure, heart rate, inflammatory biomarkers, and cortisol:

$$Y_{is} = \beta_0 + \beta_1 baseline_{is} + \beta_2 absorbed dose_{is} + \alpha_i + \varepsilon_{is}$$

Where:

- $Y_{is}$  is the observed average outcome for individual *i* at T4, and session *s* where *s* is session 1 or session 2
- $\beta_0$  is the average  $Y_{is}$  for the study population at T4, adjusted for baseline.
- $\beta_1$  is the estimated difference in  $Y_{is}$  at T4 between two groups differing in baseline by 1 unit, adjusted for absorbed dose.
- $\beta_2$  is our primary coefficient of interest and is the estimated difference in  $Y_{is}$  between two groups differing in absorbed dose by 1 unit, adjusted for baseline.
- $\alpha_i$  is the random intercept for subjects to account for repeated measures within individuals
- $\varepsilon_{is}$  is the observation-specific error

For positive and negative affect levels (SF-PANAS):

 $Y_{is} = \beta_0 + \beta_1 baseline_{is} + \beta_2 absorbeddose_{is} + \beta_3 missingscale item_{is} + \alpha_i + \varepsilon_{is}$ 

Where:

- $Y_{is}$  is the observed average outcome for individual *i* at T2, and session *s* where *s* is session 1 or session 2
- $\beta_0$  is the average  $Y_{is}$  for the study population at T2, adjusted for baseline, missing scale items, and absorbed dose.
- $\beta_1$  is the estimated difference in  $Y_{is}$  at T2 between two groups differing in baseline by 1 unit, adjusted for missing scale items and absorbed dose.
- $\beta_2$  is our primary coefficient of interest and is the estimated difference in  $Y_{is}$  between the two groups differing in absorbed dose by 1 unit, adjusted for baseline and missing scale items.
- $\beta_3$  is the estimated difference in  $Y_{is}$  between two groups differing in missing affect scale items by 1 item, adjusted for baseline and absorbed dose.
- $\alpha_i$  is the random intercept for subjects to account for repeated measures within individuals
- $\varepsilon_{is}$  is the observation-specific error

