Additionally, the clinically validated University of Pennsylvania Smell Identification Test (UPSIT) (Sensonics International, Haddon Heights, NJ) was administered to determine whether participants had anosmia/hyposmia. The UPSIT is a 40-item, self-administered "scratch-and-sniff" test that uses microencapsulated odorants that are released by scratching designated spaces on a paper test booklet. Summed scores were used to evaluate olfactory function and identify/exclude participants with undiagnosed smell loss or total anosmia (summed UPSIT score ≤ 18).

Following enrollment, participants were randomly assigned to a sequence of two sessions using a computer-randomized order created by an investigator who was not a member of the field team. To control participants inhalation exposures to terpenes in the forest air, participants wore a powered air-purifying respirators (PAPRs; 3M[™] Versaflo[™] Powered Air Purifying Respirator, TR-800-PSK/94248; 3M, St. Paul, MN). In one session, the PAPR mask was fitted with a particle-only filter (3M[™] Versaflo[™] High-Efficiency Filter, TR-6710N-5) to allow for the inhalation of forest terpenes ("terpenes-on"). In the other session, the mask was fitted with a charcoal filter (3M[™] Versaflo[™] Organic Vapor/HEPA Cartridge, TR-6510N) that removed particles, terpenes, and other BVOCs from the breathing zone ("terpenes-off"). Equipment labels were covered and filters were labeled "A" (later revealed to be "terpenes-off") to blind the study field team and participants to treatment assignment. A washout period of at least eight days between sessions was included to reduce carryover effects (Sibbald & Roberts, 1998).

Forest-sitting sessions took place at the UW Charles L. Pack Experimental Forest located near Eatonville, Washington ("Pack Forest") during June to September 2022 and 2023 to avoid rain, snow, and cold weather. The sessions were 60 minutes each and took place between 10:00 AM and 4:00 PM in a stand of old- and second-growth Douglas Fir, Western Red Cedar, and other conifers accessible by a 10-minute drive on an unpaved single-lane road from the Pack Forest Conference Center. Participants were seated in a comfortable chair, but the session was otherwise unscripted.

3. Methods

We enrolled 43 adult participants between July 12, 2022, and September 21, 2023. Our target sample size of 40 participants was based on the estimated numbers needed to detect minimum differences in the study

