Here, we aim to fill a critical gap in knowledge by examining whether terpenes play a role in the health effects of nature contact in a real-world forest environment by assessing whether terpene inhalation, with a focus on the olfactory pathway, impacts stress reduction and affective outcomes using a randomized double-blind crossover trial design. The primary outcome was the HF component of HRV, a measure of parasympathetic nervous system (PNS) activity, or relaxation (add some citations to back up this claim). Secondary outcomes included measures of skin conductance levels (SCL), blood pressure, and HR (i.e., measures of sympathetic nervous system activity, or stress), self-reported stress and affect, and levels of inflammatory cytokines in serum. Terpene concentrations in serum were measured to assess the degree of association of absorbed dose with study outcomes. We predicted that exposure to forest terpenes would be associated with greater increases in HF HRV and positive affect, and greater decreases in SCL, blood pressure, HR, self-reported stress, negative affect, and levels of inflammatory cytokines in serum compared to the condition with no forest terpenes exposure. Additionally, we predicted that study outcomes would be associated with absorbed dose of forest terpenes.

To our knowledge, no study has been conducted that concurrently investigated real-world ambient terpene exposure in a forest, absorption of these terpenes, and impacts of experimental vs. control conditions of these terpene exposures on psychophysiological and immunological effects in human beings. Therefore, this study aims to further scientific understanding of the role that forest terpene inhalation exposures play in the multisensory pathways that link human well-being and forest exposure.

5. References

Aoshima, H., & Hamamoto, K. (1999). Potentiation of GABA Receptors Expressed in Xenopus Oocytes by Perfume and Phytoncid. *Bioscience, Biotechnology, and Biochemistry*, *63*(4), 743–748. https://doi.org/10.1271/bbb.63.743

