# 2. Specific Aims

2. 1. Aim 1. Assess whether VOC inhalation regulates stress reduction and affective outcomes of the terpenes-on vs. terpenes-off sessions.

Primary physiological outcome: increases in the HF (ms) component of HRV.

Secondary outcomes: decreases in blood pressure, heart rate, self-reported stress, negative affect, and levels of inflammatory cytokines (IL-6, TNF-alpha, CRP) and cortisol in serum, and increases in positive affect, measured via mobile physiology equipment and blood using standard clinical methods.

Hypothesis: VOC inhalation will regulate increases in the HF (ms) component of HRV and decreases in blood pressure, heart rate, self-reported stress, and levels of inflammatory cytokines in serum as secondary outcomes.

2. 2. Aim 1a. Assess the degree of association of absorbed dose of seven forest-derived VOCs in serum (i.e.,  $\alpha$ - pinene,  $\beta$ -pinene,  $\beta$ -myrcene,  $\Delta$  3- carene, limonene,  $\beta$ - carophyllene,  $\alpha$ -humulene) with these outcomes.

Hypothesis: Absorbed dose of seven forest-derived VOCs in serum will be associated with stress reduction and affective outcomes.

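### The absorbed-dose models omit the filter, so a filter effect by another route can pass for a dose association in any terpene whose serum change differs by filter

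*SAP*

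**What the plan says.** SAP 2 (Specific Aims) states the Aim 1a hypothesis: "Absorbed dose of seven forest-derived VOCs in serum will be associated with stress reduction and affective outcomes". SAP 3.3 defines absorbed dose as the change in serum terpene from baseline to T4 and gives two models. For most outcomes the terms are an intercept, the outcome's baseline, absorbed dose and a random subject intercept. For SF-PANAS affect the number of missing items is added. The dose coefficient is named as the primary coefficient of interest and is read as the difference "between two groups differing in absorbed dose by 1 unit, adjusted for baseline", or, for affect, "adjusted for baseline and missing scale items".

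Neither model contains the filter, and sessions under both filters enter together. The primary models and the full secondary models elsewhere in the SAP do include a filter term. No filter-adjusted, within-condition or mediation analysis of dose is planned.

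Protocol 2 (Design) describes the charcoal cartridge of the terpenes-off session as one "that removed particles, terpenes, and other BVOCs from the breathing zone". Protocol 4 (Relevant Scientific Background) says the trial pursues its question "by assessing whether terpene inhalation, with a focus on the olfactory pathway". The same section treats smell and uptake into blood through the lungs as separate routes.

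**The concern.** The randomised filter affects serum dose and may also affect the outcome directly, through odour or through vapours not measured in serum. Air was analysed for 22 terpenes, whereas Aim 1a names seven in serum (Protocol 3, Methods, lists six, without α-humulene). A variable that moves both the exposure and the outcome, and is left out of the model, biases the exposure coefficient.

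An effect that bypasses serum is one of the protocol's own hypotheses. If it exists, a non-zero dose coefficient in SAP 3.3 may only restate the filter contrast, yet it could be taken as separate support for absorbed terpenes. Several terpenes could show it together and seem to corroborate one another.

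Splitting dose into within-person and between-person parts does not remove the problem. For a participant with two sessions, the within-person dose difference is itself the on-minus-off difference.

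**Working it through.** **Inputs from the documents.** 43 enrolled (Protocol 3) less 5 removed (SAP 4.2) leaves 38. SAP 4.1 counts 138 rumination forms and refers to one other time point on the same day. At two forms per session, 138 / 2 = 69 sessions. Then 38 × 2 − 69 = 7, which fits 31 participants with two sessions and 7 with one (31 × 2 + 7 = 69). This split is inferred, not stated.

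**Inputs not in the documents, so assumed and varied.** These are the size of any filter effect outside serum dose, the separation of serum dose between filters, and the spread of dose within a filter condition. The target of 40 participants comes without alpha, power or effect size. It cannot be reproduced, and nothing here depends on it.

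**Step 1: algebra.** Let F be the filter (0/1, balanced), D the dose, τ the effect of F on the outcome by a route other than D, and let the true dose effect be 0. Without F in the model,

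E[β_dose] = τ · Cov(F, D) / Var(D).

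Put D in units of its within-condition SD, with on-minus-off mean difference m. Then Cov(F, D) = m/4 and Var(D) = 1 + m²/4. Take τ = 0.63 residual SD, which is 0.63/√2 ≈ 0.45 SD of the paired difference:

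- Filter–dose correlation r = 0 (m = 0): coefficient 0.
- r = 0.5 (m = 1.15): 0.63 × 0.2875 / 1.331 = 0.136.
- r = 0.9 (m = 4.13): 0.63 × 1.0325 / 5.264 = 0.124.

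The bias is zero if either τ or m is zero, and otherwise is not.

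**Step 2: simulation over r.** Random-intercept model, 31 pairs + 7 singles, seven terpenes, τ = 0.63, dose inert, 300 runs per setting:

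| r | Mean dose coefficient | A given terpene significant | All seven significant |
|---|---|---|---|
| 0 | about 0 | 8% | 0% |
| 0.3 | 0.09 | 11% | 0.3% |
| 0.5 | 0.15 | 24% | 1% |
| 0.7 | 0.17 | 41% | 10% |
| 0.9 | 0.13 | 58% | 42% |

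With filter added, the mean coefficient is about 0 at every r and rejection is 6–8%. With τ = 0 and no filter term, rejection is 5–9%, so the Wald test is slightly liberal in its own right.

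**Step 3: simulation over the off/on dose ratio.** Filter-only effect of 0.5 SD of the paired difference. Dose = person uptake × day factor × (1 if on, the ratio if off), with log-normal CVs of 0.3–0.8 for person and 0.3–0.6 for day. Each range runs from widely spread dose (low end) to tightly spread dose (high end):

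| Off-session dose as share of on-session dose | SAP 3.3 model declares a dose association |
|---|---|
| 10% | 40–68% |
| 50% | 17–52% |
| 80% | 6–17% |

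With filter in the model the rate is about 5%.

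**Step 4: what adjustment costs.** Now let the effect act wholly through absorbed dose, again 0.5 SD, with off-session dose at 10%. Power without and then with filter:

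- CVs 0.3/0.3: about 89%, then 32%.
- CVs 0.5/0.4: about 93%, then 63%.
- CVs 0.8/0.6: about 95%, then 83%.

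In the Step 2 setting at r = 0.9, the standard error of the dose coefficient rises from 0.058 to 0.141 (0.141/0.058 ≈ 2.4 times).

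**The case against.** The strongest reply is that Aim 1a promises only an association. Nowhere do the documents say that it separates absorption from smell, and they do not call it a dose-response analysis. If serum dose is read as a marker of exposure, the unadjusted coefficient is a legitimate marginal association, and in these simulations that association does exist. This stands: the model is not invalid for that purpose. The fault arises when the coefficient is taken as evidence about absorbed dose beyond the filter.

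Second, the separation of serum dose by filter is unknown. Protocol 4 lists skin and gut as further routes, which a respirator does not control. The 24-hour avoidance request shows that other sources were expected. This also stands, and it is why the results are given over a range. Against it, the filtered car air and the zero filter before the session were meant to make the change in serum depend on the assigned filter.

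Third, adjustment gives up the randomised variation in dose and can cost much power. This stands in part. Filter is upstream of dose and is not a mediator, so adjusting for it does not block a dose effect. The precision given up comes from the filter contrast and cannot distinguish the routes. The loss is still large enough that the adjusted slope should not replace the planned one.

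**Conclusion.** The concern holds within limits. For any serum terpene whose baseline-to-T4 change differs by filter, the SAP 3.3 coefficient mixes an absorbed-dose association with whatever the filter does by other routes, and nothing in the plan separates the two. Under a filter-only effect of 0.5 SD and the inferred 69 sessions, the chance of declaring a dose association runs from about 6% to 68%, depending mainly on a separation the documents do not report. Both the effect size and the separation are assumptions.

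Three stronger readings are not supported:

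- A reader might infer that every serum terpene will show a spurious association. A terpene that does not differ by filter picks up no bias, and even at r = 0.9 all seven were significant together in only 42% of runs.
- A reader might infer that the planned result must be biased. If the filter has no effect outside serum dose, there is no bias.
- A reader might infer that the filter-adjusted slope should be the sole test of Aim 1a. The aim is worded as association, and the loss of power argues for showing both.

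**What to change.** Fit each of the two SAP 3.3 models a second time with the filter indicator added, and report the dose coefficient and its confidence interval with and without it, side by side. State in the SAP that the unadjusted coefficient is a marginal association that includes the filter effect. State also that a dose association beyond the filter contrast will be claimed only if the adjusted coefficient supports it. Report serum change by filter for each terpene, so that readers can judge the separation.

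The cost is one extra term per model on data already collected. The adjusted slope rests on dose differences within filter condition, so it is observational and must be described that way. It is also less precise, so a null adjusted slope must not be read as evidence against absorption. SAP 3.3 is written in the future tense, but the documents do not settle whether the analysis has been run. If it has, the adjusted model should be labelled as added afterwards.
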